### 7.1.1 Seizure Assessments

Seizure frequency by type and duration (<2 minutes, 2-10 minutes, >10 minutes) will be recorded daily by the parent/caregiver in a diary. Seizure types include:

- A: Hemiclonic (note lateralization right body, left body, or independent right and left)
- B: Focal With or Without Retained Awareness
- C: Secondarily Generalized Tonic Clonic (evolving to bilateral convulsive seizure from focal seizure)
- D: Generalized Tonic Clonic Convulsion
- E: Absence or Atypical Absence
- F: Myoclonic
- G: Tonic
- H: Atonic
- I: Clonic
- J: Tonic/Atonic (cannot differentiate)
- K: Infantile Spasms (if under 3 years of age)
- L: Epileptic Spasms (if 3 years of age and older)
- O: Other

Efficacy endpoints that will be derived from the diary data include frequency of convulsive seizures and of all seizures, and the number/duration of seizure free intervals.

Seizures that evolve into SE will be captured by type and duration (>10 minutes) as are all seizures. The diagnosis of SE made by a medical professional should be entered as an SAE if a prolonged seizure or series of seizures persists for 30 minutes or longer, regardless of administration of rescue medication. SE lasting for less than 30 minutes should be entered as an AE, unless one of the other SAE criteria (e.g. hospitalization) are met. If this incident involves multiple seizures close in time, the SE definition applies if the seizures are close together such that consciousness is not regained between ictal events.

Confidential Page 63 of 175

### 7.1.2 Clinical Global Impression - Improvement

Both the parent/caregiver and the investigator will rate their global impression of the subject's condition throughout the study according to the schedule in Table 1.

The CGI scale measures the change in the subject's clinical status from a specific point in time, ie, the Baseline Period. The CGI rating scale permits a global evaluation of the subject's improvement over time. The severity of a patient's condition is rated on a 7-point scale ranging from 1 (very much improved) to 7 (very much worse) as follows:

1=very much improved 2=much improved 3=minimally improved 4= no change 5=minimally worse 6=much worse 7=very much worse

The parent/caregiver will be asked to indicate the appropriate response that adequately describes how their child's symptoms have improved or worsened relative to baseline before the beginning of the study (before any study drug was taken).

The investigator will be asked to indicate the appropriate response that adequately describes how the subject's symptoms have improved or worsened relative to baseline before the beginning of the study (before any study drug was taken). A paragraph describing symptoms and function at baseline will be document in the source file prior to rating.

## 7.1.3 Quality of Life in Childhood Epilepsy Scale

The QOLCE (Appendix 4), a low-burden parent/caregiver completed assessment that looks at how epilepsy affects day-to-day functioning of their child in various life areas, including physical activities, well-being, cognition, social activities, behavior and general health, will be conducted according to the schedule in Table 1. The QOLCE has been validated in children aged 4 and older, and there are published data on the use of the QOLCE in children with epilepsy as young as 2 years of age (Sabaz 2000; Talarska 2007).

# 7.14 PedsQL Quality of Life Inventory (PedsQL)

The PedsQL (Appendix 6) is a pediatric modular measure of health-related QoL completed by the parent/caregiver on behalf of the subject. It consists of 4 core scales that measure physical, emotional, social, and school functioning. The PedsQL will be conducted according to the schedule in Table 1.

### 7.1.5 Parent/Caregiver Quality of Life

The impact on the quality of life of the parent/caregiver responsible for a patient with DS will be assessed according to the schedule in Table 1 using 3 scales: the EQ-5D-5L, the HADS, and

Confidential Page 64 of 175

the PedsQL Family Impact Module. Parents/caregivers who do not give consent to collect these ratings scales will not complete them. The same parent/caregiver should complete these ratings throughout the study. If that person is not available at the visit, the scales should not be completed.

The EQ-5D-5L (Appendix 7) is a standardized measure of health status used to provide a simple, generic assessment for clinical and economic appraisal. It consists of 6 questions and can be completed in less than 10 minutes.

The HADS (Appendix 8) is a tool commonly used to determine the levels of anxiety and depression that a person is experiencing. It is a 14-item scale that generates ordinal data. Seven of the items relate to anxiety and 7 relate to depression.

The PedsQL Family Impact module (Appendix 6) is designed to measure the impact of pediatric chronic health conditions on parents and the family by measuring parent self-reported physical, emotional, social, and cognitive functioning, communication, worry, and family daily activities relationships. This module will not be used in Norway, Sweden, and Denmark.

The parent/caregiver will be asked to indicate the appropriate response that adequately describes how the care of their child with DS has impacted their quality of life using the scales described above.

### 7.2 SAFETY ASSESSMENTS

# 7.2.1 Demographics, Medical/Neurological/Epilepsy History, and Pre-Study Medication

Subject demographics (sex, age, height, weight, and BMI), all ongoing conditions and relevant medical history from the past 5 years (including all major hospitalizations and surgeries) as well as the subject's current medical status will be recorded at the Screening visit. Significant medications taken during the 30 days prior to the Screening visit will be documented.

Medication history will be updated as outlined in Table 1.

### 7.2.2 Physical Examinations

Complete and abbreviated physical examinations, including height and weight, will be conducted by the investigator or designee during the study as outlined in Table 1. A complete standard of care physical examination for each subject will be performed and will cover the following body systems: general appearance, skin, eyes, ears, nose, throat, heart, lungs, abdomen, neurological system, lymph nodes, spine, and extremities. An abbreviated physical examination for each subject will cover the following body systems: heart, lungs, and follow up of other systems as appropriate based on last exam and reported AEs.

Any unfavorable findings not present at screening considered by the investigator as clinically significant, occurring at any point in the study will be documented in the eCRF as an AE.

### 7.2.3 Neurological Examinations

Confidential Page 65 of 175

Complete and abbreviated neurological examination will be conducted by the investigator or designee during the study as outlined in Table 1. A complete standard of care neurological examination for each subject will be performed and will cover the following: cranial nerves, muscle strength and tone, reflexes, coordination, sensory function, and gait. An abbreviated neurological follow-up examination for each subject will evaluate any symptoms or systems found to be abnormal and unstable or potentially unstable that might evolve during study treatment, or to investigate any reported or observed AEs.

Any unfavorable findings not present at screening considered by the investigator as clinically significant, occurring at any point in the study will be documented in the eCRF as an AE.

### 7.2.4 Vital Signs

Vital signs including blood pressure, heart rate, temperature, and respiratory rate will be documented for subjects during study as outlined in Table 1.

## 7.2.5 Laboratory Measurements

Laboratory safety parameters will be analyzed using standard validated methods.

The following parameters will be assessed by the laboratory as described in Table 1:

- Hematology: hemoglobin, hematocrit, erythrocytes, erythrocyte mean corpuscular volume, leukocytes, mean corpuscular hemoglobin, mean corpuscular hemoglobin concentration, neutrophils, lymphocytes, monocytes, eosinophils, basophils and platelets
- Blood Biochemistry: albumin (ALB), alkaline phosphatase (AP), alanine aminotransferase (ALT; SGPT), aspartate aminotransferase (AST; SGOT), bicarbonate, blood urea nitrogen (BUN), calcium (Ca), carbon dioxide (CO₂), chloride (Cl), creatinine, creatine kinase, gamma-glutamyl transferase (GGT), globulin, glucose, lactate dehydrogenase (LDH), phosphorus, potassium (K), sodium (Na), thyroid function (T3, T4, and thyroid stimulating hormone [TSH]),

Confidential Page 66 of 175

total bilirubin, direct bilirubin, total cholesterol, total protein, triglycerides, uric acid.

- Tests of growth and precocious puberty: Growth hormone (GH), insulin-like growth factor-1 (IGF-1, low sensitivity), prolactin, Luteinizing Hormone (LH), Follicle Stimulating Hormone (FSH), testosterone, estradiol
- Epilepsy genotype panel
- Coagulation: Prothrombin time (PT)/International normalized ratio (INR), activated partial thromboplastin time (PTT)
- Whole blood cannabidiol
- Urinalysis: analysis for pH, glucose, ketones, nitrite, protein, bilirubin, urobilinogen, leukocyte esterase, and occult blood. Microscopic analysis will be performed for blood, all cell types, and casts.
- Urine pregnancy test: Urine pregnancy testing will be performed in female subjects of childbearing potential.
- Urine THC panel

The investigator will receive the laboratory report from the central laboratory. After reviewing the report and evaluating any results that are outside the normal range, the investigator must sign and date the laboratory report.

Tests resulting in abnormal laboratory values that have been classified by the investigator as abnormal, clinically significant should be repeated as soon as possible after receiving the laboratory report to rule out laboratory errors.

At Screening any laboratory values that deviate from the reference ranges and are considered by the investigator as clinically relevant must be documented on the medical history form of the eCRF. Any deviation outside of the reference range considered by the investigator as clinically significant (ie, classified as an abnormal, clinically significant value) at any visit after screening will be documented in the eCRF as an AE (see Section 9).

### 7.2.6 Plasma Sample for Concomitant Antiepileptic Drug(s)

Plasma samples to ensure that concomitant antiepileptic drug(s) (AEDs) dosing is within an acceptable range will be conducted during the study as outlined in Table 1. Samples collected

Confidential Page 67 of 175

at Visit 6 will be analyzed after collection as a safety measure. Samples collected at other time points will be analyzed at study end and do not constitute safety assessments.

### 7.2.7 Electrocardiograms

Twelve-lead ECGs will be conducted during study as outlined in Table 1 after the subject has been in the supine position resting for ≥5 minutes. Heart rate, PR duration, QRS duration, QT duration, QTcF (Fridericia's correction formula), and the investigator's overall interpretation will be recorded.

### 7.2.8 Doppler Echocardiography

Doppler echocardiography will be conducted at a facility with experience for the subject's age during study as outlined in Table 1. Doppler echocardiography uses ultrasound technology to examine the heart or blood vessels. An ECHO uses high frequency sound waves to create an image of the heart while the use of Doppler technology allows determination of the speed and direction of blood flow by utilizing the Doppler effect. Predetermined standard guidelines on the proper evaluation of certain measurements, as well as abnormality thresholds, were constructed by the sponsor's IPCAB prior to study initiation. These thresholds are provided in Table 9 (Adverse Events of Special Interest). A manual of proper ECHO technique for sites is provided in a separate document.

### 7.2.9 Tanner Staging

Tanner Staging (Appendix 5) will be assessed for subjects >7 years old during the study as outlined in Table 1. Conceptually, pubertal maturation can be described in terms of sequence, timing, and tempo. Puberty consists of a series of predictable events, and the sequence of changes in secondary sexual characteristics has been categorized by several groups. The staging system used most frequently was published by Marshall and Tanner (1969, 1970) and the sequence of changes are commonly referred to as 'Tanner stages'.

### 7.2.10 Columbia-Suicide Severity Rating Scale

C-SSRS (Appendix 2) will be assessed during study as outlined in Table 1. The C-SSRS is a validated rating scale that assesses suicidal behavior and ideation. The scale is used to assess and track suicide events and provides a summary measure of suicidal tendency. The C-SSRS version 6/23/10 (Children's Baseline/Screening and Children's Since Last Visit) will be used in this study as appropriate for the age and level of intellectual development.

Subjects who are younger than 7 years chronologically, or who are judged by the investigator not to have the mental capacity to understand the questions as specified on the C-SSRS, will

Confidential Page 68 of 175

not complete the rating. The investigator should use his/her judgment to substitute intellectually-appropriate questions to probe the tendency for self-harm.

If a subject with the intellectual capacity to complete the C-SSRS has their 7th birthday during the study, use of the C-SSRS should be initiated at subsequent visits.

### 7.2.11 Adverse Events

Adverse events will be collected from the time of signing the informed consent form/assent form until the end of the study, including the follow-up clinic visit. Details of the definitions and categorization of AEs, and procedures for the reporting of AEs, are available in Section 9.

Severity and causality of AEs will be evaluated according to the criteria specified in Section 8.2 and Section 8.3, respectively. The observation period for AE reporting is specified in

Section 8.4. At the beginning of each visit at the study site, the study personnel will specifically inquire about any AEs that might have occurred since the last study site visit. All AEs will be recorded on the appropriate eCRF page.

### 7.2.12 Behavior Rating Inventory of Executive Function (BRIEF)

The BRIEF is a standardized, validated rating scale to measure executive function in children ages 2-18 years within the home and school environments; it will be assessed according to the schedule in Table 1. The BRIEF measures multiple aspects of executive functioning; scales include Inhibit (control impulses; stop behavior), Shift (move freely from one activity/situation to another; transition; problem-solving flexibility), Emotional Control (modulate emotional responses appropriately), Initiate (begin activity; generate ideas), Working Memory (hold information in mind for purpose of completing task), Plan/Organize/Organization of Materials (anticipate future events; set goals; develop steps; grasp main ideas), and Monitor (check work; assess own performance).

### 7.3 PHARMACOKINETIC ASSESSMENTS

Blood samples for PK assessments of fenfluramine and its metabolite (norfenfluramine) will be obtained from all subjects via an indwelling cannula or by venipuncture.

Blood samples for PK assessment (2 mL) will be obtained at the following time points:

• Maintenance Period Study Day 43: within 1 hour prior to the morning dose, and 1, 2, and 4-6 hours after the morning dose.

A total of 4 PK samples will be drawn for each subject for a total of approximately 8 mL of blood

When blood draws for PK coincide with other assessments, the PK draws take precedence.

The procedure for the collection and handling of PK samples is outlined in a separate study manual.

Confidential Page 69 of 175

#### 7.4 APPROPRIATENESS OF MEASUREMENTS

All of the variables assessed are standard tests or procedures that are commonly used in studies of this type.

#### 8. ADVERSE EVENTS

#### 8.1 **DEFINITIONS**

#### **8.1.1** Adverse Events

According to ICH guidelines, an AE is any untoward medical occurrence in a patient or clinical investigation subject administered a pharmaceutical product and which does not necessarily have a causal relationship with this treatment. An AE can, therefore, be any unfavorable and unintended sign (including an abnormal, clinically significant laboratory finding), symptom, or disease temporally associated with the use of a medicinal (investigational) product, whether or not considered related to the medicinal (investigational) product. The period of observation for adverse events extends from the time the subject gives informed consent until the end of study.

#### Adverse events may include:

- Exacerbation (ie, an increase in the frequency or severity) of a pre-existing condition. Illness present before study entry should be recorded in the medical history section of the eCRF and only be reported as an AE if there is an increase in the frequency or severity of the condition during the study. Exacerbation of seizures is considered an AE if there was an increase in frequency beyond the subject's typical pre-study fluctuations, or in the event that seizures lengthen in duration in a clinically meaningful way compared with baseline, or if a new seizure type emerges.
- A clinical event occurring after consent but before IMP administration.
- Intercurrent illnesses with an onset after administration of IMP.

# Adverse events do not include:

- Medical or surgical procedures (the condition that leads to the procedure is the AE, eg, tonsillitis is the AE if a tonsillectomy is performed)
- Situations where an untoward medical occurrence has not taken place. For example:
  - o Planned hospitalizations due to pre-existing conditions, which have not worsened.
  - Hospitalizations that occur for procedures not due to an AE (eg, cosmetic surgery).
  - Hospitalizations for a diagnostic procedure where the hospital stay is less than 24 hours in duration or for normal management procedures (eg, chemotherapy).

For laboratory safety parameters, any instances of absolute values being outside the reference range or changes at any visit after study start that are considered by the investigator as clinically significant must be recorded in the eCRF as AEs. In addition, at the investigator's

Confidential Page 70 of 175

discretion, any changes or trends over time in laboratory parameters can be recorded in the eCRF as AEs if such changes or trends are considered to be clinically relevant, even if the absolute values are within the reference range.

Laboratory findings do not need to be reported as AEs in the following cases:

- 1. Laboratory parameters are already beyond the reference range, unless a further increase/decrease can be considered an exacerbation of a pre-existing condition.
- 2. Abnormal laboratory parameters caused by mechanical or physical influences on the blood sample (eg, hemolysis) and flagged as such by the laboratory in the laboratory report.
- 3. Abnormal parameters that are obviously biologically implausible (eg, values that are incompatible with life).
- 4. An abnormal laboratory value that cannot be confirmed after a repeated analysis, preferably in the same laboratory (eg, the previous result could be marked as not valid and should not necessarily be reported as an AE).

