# 10.5.2 Safety Analyses

Summaries of safety data will be presented by treatment – ZX008 0.8 mg/kg/day, ZX008 0.2 mg/kg/day or placebo – separately for the Titration, Maintenance and T+M periods. The number and percentage of subjects in each treatment group with AEs will be displayed by body system and preferred term using the Medical Dictionary for Regulatory Activities (MedDRA). Summaries of AEs by severity and relationship to study drug will also be presented. A separate summary will be provided for all serious AEs (SAEs). Selected summaries will be repeated broken out by age group, ie, for ages <6 years and ≥6 years.

Hematology and chemistry laboratory results will be summarized using shift tables that tabulate the

Confidential Page 85 of 175

proportion of subjects who have lab results that change from baseline. Shift tables will be presented for each time point where lab results are collected. Mean change from baseline will also be calculated for continuous hematology and chemistry results at all time points available.

Laboratory tests, vital signs, physical examinations, neurological examinations, ECG, Doppler echocardiogram, C-SSRS, Tanner Staging results, etc, will be summarized appropriately, by treatment. All safety summaries will be based on the SAF Population.

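### Section 8.1.1 item 4 lets a clinically significant laboratory value go unreported as an AE on a non-confirming repeat alone, with no requirement for same-specimen re-assay or evidence of error

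*Protocol*

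**What the plan says.** Section 7.2.5 (Laboratory Measurements) gives two instructions on clinically significant abnormal values. The test "should be repeated as soon as possible after receiving the laboratory report to rule out laboratory errors". For recording, it starts from "Any deviation outside of the reference range considered by the investigator as clinically significant" and continues "ie, classified as an abnormal, clinically significant value) at any visit after screening will be documented in the eCRF as an AE". No exception is stated, and the sentence refers the reader to Section 9, which is Data Handling Procedures.

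Section 8.1.1 states the same duty. Out-of-range values or "changes at any visit after study start that are considered by the investigator as clinically significant must be recorded in the eCRF as AEs". It then opens a list: "Laboratory findings do not need to be reported as AEs in the following cases". Item 2 covers sample artefacts such as hemolysis that the laboratory has flagged. Item 3 covers obviously implausible values. Item 4 covers "An abnormal laboratory value that cannot be confirmed after a repeated analysis, preferably in the same laboratory", and adds that "the previous result could be marked as not valid and should not necessarily be reported as an AE".

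Table 10 defines several AESIs by laboratory value: prolactin at or above twice the upper limit, fasting glucose at or above twice the upper limit, and hypoglycemia against the Day -1 value or the lower limit. It states no confirmation step for them.

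**The concern.** The repeat has one stated purpose, to rule out laboratory error. Item 4 attaches a wider consequence to it: failure to confirm is enough to release the value, whatever the reason for the failure. If the repeat is run on a new specimen, a normal result is equally what one would see if the abnormality was real and has since resolved. Resolution and error are different things, and item 4 cannot tell them apart.

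At stake is the completeness of the AE record in a pediatric safety comparison. What a site enters as an AE is settled by the protocol at the time of entry. An event that was never entered cannot be recovered by any later analysis rule. Repeats are also ordered only for values judged abnormal and clinically significant, so any correction runs in one direction.

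**Working it through.** The plan gives no figure on this point to reproduce, so the main check is a comparison of the text.

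**1. Scope of the two rules.**

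| | Section 7.2.5 | Section 8.1.1 item 4 |
|---|---|---|
| Value covered | Any clinically significant out-of-range value after screening | Any abnormal value not confirmed on repeat |
| Action | Record as AE | May be marked not valid; need not be an AE |
| Condition on the repeat | After the report is received, as soon as possible | Same laboratory preferred; specimen and timing not stated |
| Evidence of error required | Error is the stated reason for repeating | None |
| Link to the other rule | Points to Section 9 | None |

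A site working from 7.2.5 is not led to item 4. A site working from 8.1.1 may apply it. The same child could therefore be recorded differently at two sites.

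**2. Can the repeat be a new draw?** The investigator must first receive and review the central laboratory's report and classify the value. Only then is the repeat ordered. Nothing in either section confines it to the retained specimen, and a preference for the same laboratory implies that another one is allowed. A new draw is therefore permitted and plausible. The protocol gives no turnaround time, so the delay is unknown.

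**3. Would the abnormality be seen again?** Table 8 puts post-dose chemistry draws on Days 15, 43, 71 and 99.
- Spacing: 43 − 15 = 71 − 43 = 99 − 71 = 28 days.
- Below 13.5 kg, the Day 43 chemistry and hematology draw is normally skipped: 71 − 15 = 56 days.

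A short-lived abnormality set aside after one negative repeat may not be seen at the next scheduled draw.

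**4. Illustration only.** Assume true transient rates of 20% on drug and 5% on placebo, 35 children per arm (the planned size), and a share c of real abnormalities that is confirmed and therefore recorded. Expected count = 35 × rate × c. Difference = (20 − 5) × c points.

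| c | Drug | Placebo | Difference (points) |
|---|---|---|---|
| 100% | 7.0 | 1.75 | 15 |
| 75% | 5.25 | 1.31 | 11.25 |
| 50% | 3.5 | 0.88 | 7.5 |
| 25% | 1.75 | 0.44 | 3.75 |
| 0% | 0 | 0 | 0 |

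While any are recorded, the expected risk ratio stays at 20/5 = 4. Counts and absolute differences shrink. The documents supply neither the rates nor c, and the model assumes that every unconfirmed value was real and was left unreported. It shows the direction of the effect and does not estimate its size.

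**The case against.** The strongest reply is that this is a general rule with listed exceptions. Section 8.1.1 repeats the duty in 7.2.5 before listing its exemptions. The reference in 7.2.5 to Section 9 looks like an outdated number for the AE section, since 7.2.11 also sends readers to Section 9 for AE definitions. On that reading 7.2.5 defers to the section that holds item 4. This largely stands: a flat contradiction is more than the text shows. What remains is an exception that 7.2.5 neither states nor correctly points to.

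A reader might also infer more than the documents support:

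- **That transient drug effects necessarily drop out.** Item 4 is permissive. An investigator who believes the change was real and clinically significant is still under the recording duty in 8.1.1. Events may be lost; the text does not make it certain.
- **That item 4 mainly removes real events because items 2 and 3 already cover errors.** They do not cover all of them. Item 2 needs a laboratory flag and item 3 needs obvious implausibility. Unflagged hemolysis, mislabeled tubes and plausible analytical outliers fall outside both, so item 4 has a legitimate role.
- **That the laboratory tables are affected.** Section 10.5.2 says "Mean change from baseline will also be calculated for continuous hematology and chemistry results at all time points available", and nothing there removes a result marked not valid. Handling of repeat values is ordinary SAP content, and the SAP is not at hand.
- **That a dilution figure measures the loss.** Every input to such a figure is assumed.

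It is also fair that all arms are blinded under one rule, that laboratory data are summarized descriptively, and that no primary or key secondary endpoint is touched. None of this answers the central point: item 4 is wider than the purpose 7.2.5 gives for the repeat.

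**Conclusion.** The concern holds in a limited form. As written, item 4 allows a clinically significant value to be set aside on non-confirmation alone, and a real abnormality that has merely resolved meets that condition. Laboratory-defined AESIs are exposed in the same way, because Table 10 states no confirmation step of its own and nothing exempts them from item 4.

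The consequence is possible under-counting of transient laboratory AEs in every arm and, if the drug causes such events, a smaller absolute difference from placebo. It would not by itself create a false difference. The size cannot be derived from the documents. The conclusion rests on one assumption, that at least some repeats will be new draws, which the text permits and the timing in 7.2.5 makes plausible.

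**What to change.** 1. In 8.1.1, limit item 4 to values not reproduced on re-assay of the same specimen, or attributed, with a documented reason, to laboratory or sample-handling error. The second limb is needed because re-assaying a mislabeled tube would only reproduce the mistake.
2. Add that a normal result on a later specimen is recorded as resolution of the AE, with start and stop dates, and does not invalidate the first result.
3. In 7.2.5, replace the reference to Section 9 with one to 8.1.1, so that the rule and its exceptions are read together. The same outdated reference in 7.2.11 can be corrected at the same time.

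The cost is a few sentences and no additional sampling. A few more transient laboratory AEs will be listed, and some of them will be errors that nobody could document.
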